### **7.3.2.2 Secondary Endpoints of Safety and Tolerability of MEDI-575**

Secondary safety endpoints of this study include:

- Adverse events and SAEs occurring from the signing of an ICF to 90 days after the last dose or until the subject begins another anticancer therapy, whichever occurs first.

- Changes in clinical laboratory and ECG evaluations from baseline.

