### Secondary Endpoints

- Antitumor Activity Assessments
- Assessments of other antitumor activities include objective response rate (ORR), time to response (TTR), duration of response (DR), time to progression (TTP), progression-free survival (PFS), and overall survival (OS)
- Safety and Tolerability Assessment
- Endpoints include adverse events (AEs) and serious adverse events (SAEs) occurring from the signing of ICF to 90 days after the last dose or until the subject begins another anticancer therapy, whichever occurs first, and changes in clinical laboratory and electrocardiogram (ECG) evaluations from baseline.
- Expression of PDGFR $\alpha$
- Archival tissue samples (obtained from subjects prior to trial enrollment) and, when available, fresh tumor biopsy samples (obtained from subjects following discontinuation of MEDI-575) will be evaluated using IHC. Expression of PDGFR $\alpha$  in tumor cells and/or tumor stromal cells will be evaluated for intensity and distribution of staining and relationship with clinical endpoints and circulating soluble factors associated with cancer-associated fibroblasts and/or a PDGF-AA paracrine mechanism of action. The percentage of target positive subjects will be described if there are sufficient data. Descriptive statistics will be used

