## 3 Study Design

### 3.1 Overview of Study Design

This is a Phase 2, multicenter, open-label, single-arm study to evaluate the antitumor activity, safety, and pharmacology of MEDI-575 in adult subjects with first recurrence of GBM.

Approximately 55 subjects will be enrolled to determine the preliminary efficacy profile of MEDI-575 in the treatment of subjects with first recurrence of GBM. Subjects will receive MEDI-575 as a 60-minute IV infusion on Day 1 every 21 days until disease progression, initiation of alternative anticancer therapy, unacceptable toxicity, or other reasons for subject withdrawal (see Section 4.2.3) (Figure 3.1-1). In Cycle 2 and beyond, a dose can be delayed up to 7 days for unavoidable scheduling issues. MEDI-575 may be withheld for up to 21 days until resolution to  $\leq$  Grade 1 toxicity after agreement with the sponsor. The primary assessment of antitumor activity is PFS-6; progression will be determined using *Updated Response Assessment Criteria of High Grade Gliomas- Neuro-Oncology Working Group v.1* (see Appendix 5) (Wen et al, 2010). Approximately 15 investigational sites in the United States (USA) will participate in this study. Subjects who receive any amount of MEDI-575 and proceed to subsequent surgery as therapy for GBM (at second recurrence/disease progression) will be requested to allow use of surgically resected tissue for analysis of intratumoral levels of MEDI-575.

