### **5.2.1 Screening (All Subjects)**

All screening procedures must be performed within 28 days prior to the first dose of treatment (Day -28 to Day -1), unless otherwise specified. The screening evaluations may be carried out over more than one visit. Written informed consent and any locally required authorization (eg, HIPAA in the USA, EU Data Privacy Directive authorization in the EU) must be obtained prior to performing any protocol-specified procedures, including screening evaluations. However, if evaluations that have been performed for other purposes prior to informed consent are otherwise suitable for use as screening evaluations, those evaluations need not be repeated if the subject/legal representative consents to allow use. The following evaluations/procedures will be performed during screening:

- 1) Obtain written informed consent and appropriate privacy act document authorization
- 2) Assign an SID number via IWRS
- 3) Verify eligibility criteria
- 4) Obtain medical history
- 5) Perform complete physical examination
- 6) Obtain vital signs, including height and weight (-1 day allowed for weight)
- 7) Obtain 12-lead ECG
- 8) Collect blood samples for:
  - Serum chemistry (-1 day allowed)
  - Hematology (-1 day allowed)
  - Coagulation parameters (-1 day allowed)
  - Serum pregnancy test
  - Circulating soluble proteins
  - Circulating apoptotic markers
  - Circulating messenger ribonucleic acid (mRNA)/microRNA (miRNA)
  - DNA analysis (optional)
- 9) Collect urine for screening sample (-1 day allowed)
- 10) Collect archive tissue for biomarker screening sample
- 11) Measure tumors using MRI
- 12) Assess for AEs and SAEs
- 13) Record concomitant medications

- 14) Assess for ECOG performance status
- 15) Administer Patient Reported Outcome (PRO) questionnaires (-3 days allowed):
  - European Organization of Research and Treatment of Cancer (EORTC) quality of life questionnaire (QLQ)-C30
  - EORTC QLQ-BN20
- 16) Enroll subject if all eligibility criteria are met

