## 6 Assessment of Safety

### 6.1 Safety Parameters

#### 6.1.1 Adverse Events

The ICH Guideline for Good Clinical Practice E6(R1) defines an AE as:

Any untoward medical occurrence in a patient or clinical investigation subject administered a pharmaceutical product and which does not necessarily have a causal

relationship with this treatment. An AE can therefore be any unfavorable and unintended sign (including an abnormal laboratory finding), symptom, or disease temporally associated with the use of a medicinal product, whether or not considered related to the medicinal product

An AE includes, but is not limited to any clinically significant worsening of a subject's pre-existing condition. An abnormal laboratory finding (including ECG finding) that requires an action or intervention by the investigator, or a finding judged by the investigator to represent a change beyond the range of normal physiologic fluctuation, should be reported as an AE.

Adverse events may be treatment emergent (ie, occurring after initial receipt of investigational product) or nontreatment emergent. A nontreatment-emergent AE is any new sign or symptom, disease, or other untoward medical event that begins after written informed consent has been obtained but before the subject has received investigational product.

Elective treatment or surgery or preplanned treatment or surgery (that was scheduled prior to the subject being enrolled into the study) for a documented pre-existing condition that did not worsen from baseline is not considered an AE (serious or nonserious).

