## **6.4 Reporting Requirements for Safety Parameters**

### **6.4.1 Study Reporting Period and Follow-up for Adverse Events**

The reporting period for AEs is the period immediately following the time that written informed consent is obtained through 90 days post the last dose of treatment or until the subject begins another anticancer therapy, whichever occurs first. New (nonserious) AEs that start after the reporting period will not be collected.

All AEs will be followed to resolution through the end of subject participation in the study, even if the date extends beyond the reporting period.

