## 7.2 Analysis Populations

The intent-to treat (ITT) population will include all subjects entered into the study. The ITT population is the primary population for the efficacy analyses and the summary of baseline characteristics.

The evaluable population will include all subjects who received at least 1 dose of MEDI-575 and had at least 1 post-baseline disease assessment. The evaluable subject population will be the secondary population for efficacy analysis.

The safety population will include all subjects who receive at least 1 dose of MEDI-575 and will be used to summarize the safety assessments.

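### The AE/SAE endpoint for MEDI-575 starts at consent rather than first dose, so pre-dose events of dosed subjects enter the all-cause safety summaries

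*Protocol*

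**What the plan says.** Section 7.3.2.2, under a heading that names safety and tolerability of MEDI-575, lists as an endpoint "Adverse events and SAEs occurring from the signing of an ICF to 90 days after the last dose", cut short if another anticancer therapy starts first. The Abstract repeats it: "Endpoints include adverse events (AEs) and serious adverse events (SAEs) occurring from the signing of ICF to 90 days after the last dose".

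Section 6.4.1 sets the same window for data collection: "The reporting period for AEs is the period immediately following the time that written informed consent is obtained through 90 days" after the last dose, with the same early end. Section 6.4.2.1 does likewise for SAEs.

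Section 6.1.1 draws the distinction that the endpoint leaves unused: "Adverse events may be treatment emergent (ie, occurring after initial receipt of investigational product) or nontreatment emergent". It adds: "A nontreatment-emergent AE is any new sign or symptom, disease, or other untoward medical event that begins after written informed consent has been obtained", provided that no product has yet been given.

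Section 7.2 fixes who is summarized: "The safety population will include all subjects who receive at least 1 dose of MEDI-575 and will be used to summarize the safety assessments". Section 5.2.1 bounds the pre-dose period: "All screening procedures must be performed within 28 days prior to the first dose of treatment". Section 3.1 describes the design: "This is a Phase 2, multicenter, open-label, single-arm study".

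**The concern.** Collecting AEs from consent is ordinary and right. The difficulty is that the collection window has become the endpoint by which the drug's safety is described. The safety population requires one dose, which removes subjects who were never treated. It does not remove what happened to treated subjects before their first infusion. A seizure leading to admission ten days before the first dose would, on the endpoint's wording, be one of the SAEs that describe MEDI-575.

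In a controlled trial the same inclusion would fall on both arms and could be seen. Here there is no second arm, so the all-cause percentages are the description of safety that a reader will compare with other sources. At stake is a modest upward shift in those percentages, and an endpoint that does not match the protocol's own AE categories.

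**Working it through.** The endpoint states no rate, so there is no plan figure to reproduce. The check has two parts.

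**1. Where each outcome starts**

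| Outcome | Section | Start |
|---|---|---|
| TTR, TTP, PFS, OS | 7.3.2.1 | first MEDI-575 administration |
| Duration of response | 7.3.2.1 | first documented response |
| Laboratory and ECG endpoints | 7.3.2.2 | change from baseline |
| DLTs | 4.5.4.2 | first administration |
| AE/SAE endpoint | 7.3.2.2, Abstract | signing of consent |
| AE collection | 6.4.1 | signing of consent |

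Only the AE/SAE endpoint opens before drug is given, and its window is identical to the collection window.

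**2. Illustration of size**

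Inputs from the protocol: at most 28 screening days (5.2.1), dosing every 21 days (4.5.2), a window closing 90 days after the last dose (7.3.2.2), and categorical data summarized by number and percentage of subjects (7.1).

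Assumptions, because the protocol gives no AE rate:
- a constant background rate unrelated to the drug, with chance *b* of at least one event per 28 days, *b* = 5%, 10% or 20%;
- *s* = 14 or 28 pre-dose days;
- *k* = 1 or 3 doses;
- the full 90 days observed after the last dose.

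Days from first dose: *t* = 21(*k* − 1) + 90, which is 90 for one dose and 132 for three.

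Rate: λ = −ln(1 − *b*)/28. Incidence from first dose is 1 − exp(−λ*t*). Incidence from consent is 1 − exp(−λ(*t* + *s*)).

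| *b* | Doses | From first dose | From consent, 14 days | Rise (points) | From consent, 28 days | Rise (points) |
|---|---|---|---|---|---|---|
| 5% | 1 | 15.2% | 17.3% | 2.1 | 19.4% | 4.2 |
| 5% | 3 | 21.5% | 23.5% | 2.0 | 25.4% | 3.9 |
| 10% | 1 | 28.7% | 32.4% | 3.7 | 35.9% | 7.2 |
| 10% | 3 | 39.1% | 42.3% | 3.2 | 45.2% | 6.1 |
| 20% | 1 | 51.2% | 56.3% | 5.1 | 61.0% | 9.8 |
| 20% | 3 | 65.1% | 68.8% | 3.7 | 72.1% | 7.0 |

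The rise is about 4 to 10 points with 28 pre-dose days and about 2 to 5 with 14.

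For 28 pre-dose days the rise equals *b* × (1 − incidence from first dose), for example 0.10 × (1 − 0.287) = 0.071, which agrees with the table to rounding. It therefore falls as doses accumulate. It grows if the window closes early because other therapy begins, but it can never exceed *b* itself.

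The pre-dose share of the window is *s*/(*s* + *t*). With 28 days this is 28/118 = 23.7% for one dose, 28/160 = 17.5% for three and 28/286 = 9.8% for nine. These are shares of time, not rises in the percentage of subjects affected.

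**The case against.** The strongest reply is that Section 7.1 leaves details of endpoint analyses to the SAP, which is not at hand. Section 7.3.2.2 names events and a window, with no rate or table, and the SAP could limit the tables to treatment-emergent events using the definitions in Section 6.1.1. That stands against any claim that a wrong analysis has been shown. It does not answer the point about wording: the window is fixed in the protocol, and a SAP restricted to treatment-emergent events would depart from it.

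A reader might infer that pre-dose disease or procedure events would be attributed to MEDI-575. The documents do not support that. Section 6.2.2.1 makes onset before administration a ground for judging an event not related, and one ground is enough. Section 6.2.2.2 gives SAEs caused by study procedures their own assessment. What remains exposed is the all-cause count.

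A reader might also infer that safety decisions are affected. DLTs are counted from first administration (4.5.4.2). The stopping criteria in Section 3.3 rest on product-related death, anaphylaxis to the product, the DLT rate or the medical monitor's judgement. None uses this window.

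Lastly, a ratio of pre-dose to post-dose days might be read as the inflation in incidence. It describes event counts, whereas Section 7.1 summarizes by subject, and a subject with events both before and after dosing counts once. Twenty-eight days is also a ceiling: Section 5.2.1 lets suitable evaluations done before consent stand as screening, which can shorten the interval. Nor do the entry criteria require symptoms (ECOG 0 or 1 is required), so no high background rate can be read from them.

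**Conclusion.** The point holds as a defect in the endpoint definition. Read as written, Section 7.3.2.2 and the Abstract place pre-dose events of dosed subjects in the all-cause AE and SAE summaries of a single-arm trial, and leave unused a distinction that the protocol itself makes.

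The illustrated size is moderate at most. It rests on assumed background rates, a constant hazard, full observation after the last dose and an assumed interval from consent to dosing. None of these can be replaced by a figure from the protocol.

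Severity is minor: the endpoint is secondary and descriptive, and the primary analysis does not depend on it.

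**What to change.** In Section 7.3.2.2 and in the Abstract, define the endpoint as treatment-emergent AEs and SAEs: those with onset, or with worsening of a pre-existing event, after the first administration of MEDI-575. Keep the present end of the window (90 days from the last dose, or the start of other anticancer therapy if sooner). The worsening clause is needed because Section 6.1.1 counts clinically significant worsening of a pre-existing condition as an AE, and a definition by onset alone could miss an event that began in screening and became worse on drug.

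State that nontreatment-emergent events will be listed separately. Leave the reporting periods in Sections 6.4.1 and 6.4.2.1 unchanged.

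The cost is a wording edit in two places. It needs no new assessments and no change to when AEs are collected, because AEs are already assessed at screening and at each treatment visit and dosing is recorded.

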### **7.3.2.3 Expression of PDGFR alpha**

Archival tissue samples and, when available, fresh tumor biopsy samples will be evaluated using IHC. Expression of PDGFR $\alpha$  in tumor cells and/or tumor stromal cells will be evaluated for intensity and distribution of staining and relationship with clinical endpoints and circulating soluble factors associated with cancer-associated fibroblasts and/or a PDGF-AA paracrine mechanism of action. The percentage of target positive subjects will be described if there are sufficient data. Descriptive statistics will be used to summarize data.

## **7.3.3 Exploratory Endpoints**

### **7.3.3.1 Pharmacokinetics and Immunogenicity of MEDI-575**

#### **7.3.3.1.1 Non-Compartmental Analysis**

The PK of MEDI-575 will be assessed using parameters including peak concentration ( $C_{max}$ ), time to peak concentration ( $T_{max}$ ), and area under the concentration-time curve within a dosing interval ( $AUC_{\tau}$ ) after the first dose. MEDI-575 steady state PK parameters including peak concentration ( $C_{ss, max}$ ), trough concentration ( $C_{ss, min}$ ), and time to peak concentration ( $T_{ss, max}$ ) will be estimated. All PK parameters will be estimated by non-compartmental analysis. The highest observed concentration will be recorded as  $C_{max}$  and the time to  $C_{max}$  will be recorded as  $T_{max}$ . Accumulation to steady state will be assessed as the ratio of  $C_{ss, max} \cdot C_{max}$ .

Immunogenicity results will be analyzed descriptively by summarizing the number and percentage of patients who develop detectable anti-MEDI-575 antibodies.

#### **7.3.3.1.2 Population Pharmacokinetic-Pharmacodynamic Analysis**

A population PK model will be developed using a non-linear mixed-effects modeling approach. Pharmacokinetic compartmental model incorporating both linear and target-mediated clearances will be used to characterize the PK of MEDI-575 in subjects with GBM. Sequential PK-pharmacodynamic modeling will be performed to explore the relationship between MEDI-575 exposure (antibody serum concentration) and biomarkers, such as PDGF-AA ligand in plasma. Exposure response modeling will be performed to examine the

relationship between MEDI-575 serum exposure and clinical endpoints. The impact of physiologically-relevant subject characteristics (covariates) and disease on PK, pharmacodynamic parameters (and possibly clinical endpoints) will be tested. The final population PK-pharmacodynamic model will be validated using standard techniques such as visual predictive check or bootstrapping.

### **7.3.3.2 Exploratory Analysis**

Descriptive statistics will be used to describe the exploratory analyses. The following variables may be included in the exploratory analysis:

- PDGF-AA levels at baseline and in response to MEDI-575 treatment
- Selected circulating soluble proteins such as proteins related to cancer-associated fibroblasts, angiogenesis and cytokines using multiplex proteomic analysis that may include but are not limited to PDGF, FGF, VEGF, fibronectin, osteopontin, TGF, HGF; at baseline and in response to treatment
- mRNA profiling from whole blood samples may be performed and gene expression analysis will examine the potential relationship between inhibition of PDGF-related genes, clinical activity and other circulating factors. The miRNA expression pattern in the periphery of subjects enrolled may also be examined. Circulating apoptotic markers will be measured by determining nucleosomal DNA using either ELISA assays or RT-PCR to evaluate tumor cell apoptosis in response to treatment.
- When fresh tumor biopsy samples are available (optional), an evaluation of the presence of MEDI-575 in tumor tissue will be performed
- Patient-reported outcomes as measured by the EORTC QLQ-C30 and the EORTC QLQ-BN20 will be summarized descriptively. Additionally, these endpoints will be summarized individually; with change from baseline for both domain and subscale scores by time point and change from baseline to be explored.

## **7.4 Interim Analysis**

No formal interim analysis will be performed during this trial.

## **7.5 Sample Size and Power Calculations**

The primary objective of this study is to evaluate the PFS-6 in adult subjects with a first recurrence of GBM who are treated with MEDI-575. The sample size estimation is based on the assumption that the historical PFS-6 rate in this population is  $\leq 16\%$  (null hypothesis). This is because the estimated PFS-6 rate for irinotecan single agent in recurrent GBM from a

single-arm Phase 2 trial was 15.8% (Prados, 2006). Using a 1-sample nonparametric test for survival probability (Brookmeyer and Crowley, 1982) and assuming the desired PFS-6 rate for MEDI-575 is 30%, a total of 50 subjects will provide 80% power to have a statistically significant test outcome at the 2-sided significance level of 0.1, accrual period of 12 months, and a follow-up period of 6 months. Assuming a drop-out rate of 10%, a total of 55 subjects will be required to enter this study.

Table 7.5-1 presents the power for detecting different PFS-6 rates for MEDI-575 at a 2-sided significance level of 0.1 with 50 subjects assuming a historical PFS-6 rate of 16%.

**Table 7.5-1 Power Calculation for Sample Size of 50 Subjects Based on Nonparametric Test for Survival Probability**

Sample Size	Historical PFS-6 Rate (Null Hypothesis)	Desirable PFS-6 Rate for MEDI-575	Power ( % )
50	16%	25%	55
50	16%	28%	72
50	16%	30%	80
50	16%	32%	86
50	16%	35%	92

PFS-6 - progression-free survival at 6 months

Note: Based on an accrual period of 12 months and a follow-up period of 6 months

The study will be considered positive if the lower bound of the 2-sided 90% CI for PFS-6 rate is  $\geq 16\%$ .

## 7.6 Data Safety Monitoring Board

As an open-label study, no formal data safety monitoring board will be employed. Safety monitoring will be performed by the medical monitor who will regularly review rates and types of AEs. Results will be reported to the MedImmune SMC at regular intervals.

## 8 Direct Access to Source Documents

The study will be monitored by the sponsor on a regular basis throughout the study period. During monitoring visits, the investigator will provide direct access to all source documentation relevant to the subject's participation in the study. Source documentation includes, but is not limited to, the subject's clinic and/or office chart, hospital chart, informed

consent forms, treatment notes, laboratory reports, pharmacy records, radiographs, recorded data from automated instruments, and any other records maintained to conduct and evaluate the clinical study. The investigator must also ensure that direct access to study documents be made available for study-related audits, IRB/IEC review, or regulatory inspection.

## **9 Quality Control and Quality Assurance**

### **9.1 Data Collection**

As part of the responsibilities assumed by participating in the study, the investigator agrees to maintain adequate and accurate case histories for the subjects treated under this protocol. Case histories include CRFs and supporting data including, but not limited to, signed and dated informed consent forms, progress notes, hospital charts, nurse's notes, diary cards, laboratory reports, ECG strips, etc.

Subject demographics and key/essential disease baseline characteristics thought to affect outcome, ie, stratification variables and other prognostic factors, will be collected, as available, for all subjects who provide written informed consent. For subjects who provide informed consent and were not entered/randomized into the study, the reason the subject was not entered/randomized, ie, did not meet one or more inclusion criteria, met one or more exclusion criteria, or other (eg, lost to follow-up, consent withdrawn), will also be collected.

